5.1. Numbers of Participants

5.1.1. Number to be screened: N=68

5.1.2. Number to be enrolled: N = 54

Rationale of Number Expected to be Screened:

The Study will employ a quota sampling method to enroll four groups of patients, designated as: SzNET+/EEG+, SzNET+/EEG-, SzNET-/EEG+, and SzNET-/EEG-. Importantly, only the two SzNET+ groups have a minimum enrollment goal. Thus, enrollment will stop once each of the two SzNET+ groups enroll ten patients. The logic behind the patient screening and enrollments is as below.

1. SzNET+/EEG- Strata: To successfully complete the study treatment in 10 EEG- subjects, who would eventually be found to be SzNET+, we need to enroll 11 subjects, as we anticipate a 1 in 10 subject attrition. In our preliminary SABI data (Fig 2), of those who would meet inclusion/exclusion criteria, 30% with EEG- were SzNET+. Thus, we expect to need to enroll approximately 37 EEG- patients with completed good quality studies. Lastly, due to the ICU environment and the Barthel score required, we expect 80% of the subjects eligible for enrollment, thus 46 EEG- patients will be screened to fulfill this group's recruitment goal.

2. SzNET+/EEG+ Strata: To successfully complete treatment in 10 EEG+ subjects, who would eventually be found to be SzNET+, we need to enroll 11 patients, as we anticipate a 1 in 10 subject attrition. In our preliminary SABI data (Fig 2), of those who would meet inclusion/exclusion criteria, 67% of the EEG+ were SzNET+. Thus, we expect to need to enroll approximately 17 EEG+ patients with completed good studies. Lastly, due to the ICU environment and the Barthel score required, we expect 80% of the subjects eligible for enrollment. Thus, 22 EEG+ patients will be screened to fulfill this group's recruitment goal.

Participants who drop out, are withdrawn, or have missing data will not be replaced until second aim's data is complete, afterwards we will continue recruitment until we meet the two strata proposed enrollment. The subjects analyzed for the second aim will only include those scanned until the time when the first group of SzNET+/EEG+ or SzNET+/EEG- recruitment will be completed. By this strategy, the initial estimate of the proportion of SzNET+ subjects by EEG subgroup could be less biased, and we will guarantee the required number of subjects to start the interventional phase of the study while optimizing the total amount of initial rs-fMRI needed.

Sources of recruitment: UNCH PICU, NSICU, SICU, CTICU, CICU or MICU patients meeting study inclusion and exclusion criteria. Potential research subjects will be identified by the study team members chart screening of all the patients with EEG orders from ICU, for eligibility.

Interventional Study numbers of enrollees expected to receive the treatment regimen: Since this is a non-controlled interventional open-label pilot study, and we need a total of 20 subjects successfully to receive the study therapy AND repeat rs-fMRI, then due to intra-study attrition of 1:10, we expect to treat a total of 22 patients with the study therapy.

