Target Population	
Inclusion Criteria
 
1. Age from 18 months to 70 years.2. Suppression of consciousness related to a neurological injury..3. GCS less than 13.4. Acute brain Injury by TBI, hypoxic-ischemic Insult, cardiac arrest, or Stroke.5. 2 to 90 days from MSABI to enrollment.6. Have a routine clinical care surface EEG performed after the admission to PICU, NSICU, SICU, CTICU, CICU or MICU.7. Hospitalized at PICU, NSICU, SICU, CTICU, CICU or MICU 
Exclusion Criteria
 
1. Previous medical history of Epilepsy.2. Previous medical history of neurological conditions that lead to dependence greater than expected for age on care for basic daily activities given by Barthel Index score (BIS) less than 80.3. Brain death.4. Currently able to speak fluently.5. Currently at one's prior reported baseline mental status.6. Known allergy/Hypersensitivity or medical contraindications (like porphyria or cardiac arrhythmias) to the treatment protocol options, leaving no potential combination of drugs for the intervention without concerns for adverse events related to known preexistent conditions..7. Prisoner human subjects by medical chart review.8. Pregnant.9. Treating physician determines the patient is no candidate to receive 2 of the 5 protocol-specified ASM.

	10. Contraindications for MRI scan.
Numbers of Enrollees	
Up to 68 individuals will be screened with the goal of enrolling 54 eligible individuals and identifying a subset of 22 participants who are SzNET positive (see Study Schema, Figure 2). Using a quota sampling strategy, 11 SzNET+ patients will be recruited consecutively for each EEG+ and EEG- strata to ensure the necessary number of patients for the interventional phase of the study.

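### Section 5.1 stops enrolment at ten SzNET+ patients per stratum, but ten is the completer target; the rest of the plan, and its 54 enrolled and 68 screened, rest on eleven

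*Combined protocol and SAP*

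**What the plan says.** The stop rule is in Section 5.1, in the rationale for the number to be screened: "enrollment will stop once each of the two SzNET+ groups enroll ten patients".

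The two numbered items directly below give a different enrolment number. To have ten patients complete treatment, the EEG- item says "we need to enroll 11 subjects, as we anticipate a 1 in 10 subject attrition" and the EEG+ item says "we need to enroll 11 patients, as we anticipate a 1 in 10 subject attrition". The end of Section 5.1 gives the pooled version: "we need a total of 20 subjects successfully to receive the study therapy AND repeat rs-fMRI", and, after attrition, "we expect to treat a total of 22 patients with the study therapy".

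Other parts of the document agree with eleven per stratum, or 22 in total:

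- Synopsis: a quota of 11 per stratum, "with the goal of enrolling 54 eligible individuals and identifying a subset of 22 participants who are SzNET positive".
- Section 4 (rationale for stratification) and Section 5.5: a quota of eleven per EEG group.
- Section 6: group sizes of 32 SzNET-, 11 SzNET+/EEG+ and 11 SzNET+/EEG-.
- Section 8.3: 11 + 11 for Aim 1, an Aim 2 cut-off at 11 in whichever stratum fills first, and 22 subjects for Aims 3 and 4.
- Section 9: calculations at n = 11 and n = 22.

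On replacement, Section 5.1 says dropouts are not replaced until the Aim 2 data are complete, and that "afterwards we will continue recruitment until we meet the two strata proposed enrollment".

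**The concern.** The stop sentence attaches the completer number to the act of enrolling. Read as written, it closes a stratum one patient short of the quota and removes the only allowance for the attrition that the plan expects.

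This matters because Section 7.8 restricts dropouts' data to Aim 2. Aims 1, 3 and 4 therefore depend on patients who complete the intervention and have the second scan. A rule that decides when recruitment ends should state the same number as the target it serves.

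**Working it through.** **Inputs.** From Section 5.1: completer target 10 per stratum; attrition 1 in 10; SzNET+ rate 30% in EEG- and 67% in EEG+; 80% of screened patients eligible; stated totals 37 + 17 = 54 enrolled and 46 + 22 = 68 screened; 20 completers needed from 22 treated. From Section 6: 32 + 11 + 11. From Section 9: paired t-test, one-sided 0.05, 80% power.

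**Step 1: reproduce the plan's sizes with eleven.** Enrolled per stratum = quota / SzNET+ rate, rounded up.

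- EEG-: 11 / 0.30 = 36.7, so 37. EEG+: 11 / 0.67 = 16.4, so 17. Sum 54, as stated.
- SzNET-: 54 − 22 = 32, as in Section 6.
- Screened: 37 / 0.80 = 46.25 (stated as 46) and 17 / 0.80 = 21.25 (stated as 22). The stated figures sum to 68; as a check, 54 / 0.80 = 67.5.

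**Step 2: repeat with ten.**

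- EEG-: 10 / 0.30 = 33.3, so 34. EEG+: 10 / 0.67 = 14.9, so 15. Sum 49.
- SzNET-: 49 − 20 = 29.
- Screened: 34 / 0.80 = 42.5, so 43, and 15 / 0.80 = 18.75, so 19. Sum 62.

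| Quantity | Stated | With eleven | With ten |
|---|---|---|---|
| Enrolled | 54 | 54 | 49 |
| SzNET- | 32 | 32 | 29 |
| Treated | 22 | 22 | 20 |
| Screened | 68 | 68 | about 62 |

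Only eleven reproduces the stated figures.

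**Step 3: expected completers without further replacement.** Completers = enrolled × (1 − 0.10).

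- Ten: 10 × 0.9 = 9 per stratum, 18 in total.
- Eleven: 11 × 0.9 = 9.9 per stratum, 19.8 in total.

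If dropouts are independent (an assumption), the chance of at least ten completers in a stratum is 0.9^10 = 0.35 with ten enrolled. With eleven enrolled it is 0.9^11 + 11 × 0.1 × 0.9^10 = 0.70.

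**Step 4: effect on power.** The detectable standardised paired effect d solves P(T > t(0.95, n−1)) = 0.80, where T is noncentral t with n − 1 degrees of freedom and noncentrality d√n. At n = 11 this gives 0.806, which is the Section 9 figure. For the pooled comparison it gives 0.577 at n = 20 and 0.611 at n = 18, a difference of 0.034.

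**The case against.** The strongest reply is that this is one stray word. It is followed at once by two items that say eleven. Section 5.5, which governs selection for screening and enrolment, says eleven, and so do the synopsis, Section 6 and Section 8.3. Staff would probably work to eleven. The replacement rule also points that way, since the enrolment it calls proposed reads most naturally as the eleven derived just above it. All of this stands, and it limits the practical risk. It does not make the sentence right.

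A second reply is that ten was meant as ten completers, which fits the target of ten per stratum and 20 overall. That is a plausible intent, but the sentence speaks of enrolling, so it needs correction on this reading too.

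Four stronger readings are tempting but not supported:

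- A reader might infer that the trial will end with 18 completers and be materially underpowered. The 18 requires both a literal reading and no replacement beyond ten, and Step 4 shows a small loss even then.
- A reader might infer two competing Aim 2 cut-offs, because Section 5.1 says the Aim 2 set will "only include those scanned until the time when the first group of SzNET+/EEG+ or SzNET+/EEG- recruitment will be completed". That sentence gives no number, and Section 8.3 states 11 explicitly.
- A reader might infer that the quota should override 54 and 68. The synopsis presents 68 as an upper limit on screening, and Section 12.5 refers to a maximum enrolment. At the plan's rates, 37 EEG- patients yield eleven SzNET+ with probability 0.58, and both strata fill within 37 and 17 with probability about 0.39. Letting the quota override the totals would therefore be a design change, separate from this correction.
- A reader might infer from the 30% of all 63 pilot patients in Section 2.1 that the 37 is wrong. Section 5.1's 30% refers to pilot patients who would meet eligibility, and the figure with the counts is not available here, so no error is shown.

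**Conclusion.** The stop threshold in Section 5.1 is wrong as written. It contradicts the numbered items beneath it, five other parts of the document (synopsis and Sections 4, 5.5, 6 and 8.3), and the arithmetic behind 54 and 68.

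The shortfall is one enrolled patient per stratum, or about 0.9 expected completers per stratum (1.8 in total). This rests on the plan's 10% attrition and on no replacement beyond the stop number. The consequence for power is minor. The correction is worth making because this sentence states when recruitment ends, not because the study's conclusions are at risk.

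**What to change.** In the Section 5.1 stop rule, change ten to eleven. This agrees with every other section and leaves the stated 22, 54 and 68 as they are, since they are already built on eleven.

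Alternatively, if completers were meant, say that enrolment stops once ten patients per SzNET+ stratum have completed the intervention and the second scan. Then align the synopsis and Sections 4, 5.5, 6 and 8.3. Expected enrolment under that rule is 10 / 0.9 = 11.1 SzNET+ patients per stratum.

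In either case, add to Section 5.1 a reference to the Section 8.3 cut-off of eleven for the Aim 2 set.

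The first option costs one word and one cross-reference. The second costs edits in several sections and a check against the stated totals.

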5.2. Eligibility Criteria

This study will be done in moderate to severe acute brain injury (MSABI) patients aged 18 months to 70 years, at risk of epileptogenic activity and presenting with coma. The target population is recruited at Pediatric ICU (20 beds) and the Neuroscience ICU (22 beds) from UNC health at Chapel Hill, which acts as a tertiary referral center for patients from North Carolina and surrounding states. The Pediatric ICU treats an average of 109 patients/year with primary ICD codes for traumatic brain injury, arrest and encephalopathies & coma, which are the main codes for the target population.

In the United States, 795,000 people experience a stroke (ischemic or hemorrhagic) every year³³, and TBI causes approximately 282,000 hospitalizations and about 56,000 deaths each year³⁴. SABI from TBI, stroke, and other neurological problems require treatment in the ICU, where the incidence of Seizures is approximately 35%^{5,35}.

5.2.1. Inclusion Criteria

[figure not shown]

Fig. 1. Adult and Peds SABI EEG and Seizure Network (SN) prevalence (N=63). EEG-SN+ comprise 30% of the SABI population.

In order to be eligible to participate in this study, an individual must meet all of the following criteria:

- Age from 18 months to 70 years at ICU admission by medical chart review.
- Suppression of consciousness related to a neurological injury by medical chart review.
- GCS less than 13 at enrollment.
- Diagnosis of Acute brain injury by TBI, hypoxic-ischemic insult, cardiac arrest or stroke by medical chart review.
- 2 to 90 days from acute brain injury to enrollment time by medical chart review.
- Have a routine clinical surface EEG performed after the admission to PICU, NSICU, SICU, CTICU, CICU or MICU.
- Clinically stable to undergo MRI scan, This stability is defined by care team concept, which should be stated in the medical records.
- Hospitalized in NSICU, PICU, SICU, CTICU, CICU or MICU

5.2.2. Exclusion Criteria

Any individual who meets one or more of the following criteria will be excluded from participation:

- Previous medical history of Epilepsy by medical chart review.
- Previous medical history of neurological conditions that lead to dependence on care for basic daily activities, by BIS less than 80, examined with the patient's LAR at the time of the in person interview for obtaining the informed consent. If there is medical history of neurological conditions with concerning for impaired independence and the functional status of the patient cannot be addressed properly the patient will be excluded from participation.
- Known allergy/Hypersensitivity or medical contraindications (like porphyria or cardiac arrhythmias) to the treatment protocol options, leaving no potential combination of drugs for the intervention without concerns for adverse events related to known preexistent conditions.
- Considered with Brain death by the care team in the medical record, at any time.
- Is following Commands in 3 different exams from at least 2 different providers.
- Contraindications for MRI scan.
- Prisoner human subjects by medical chart review.
- Confirmed currently pregnant by medical history or by positive blood or urine pregnancy test done in the present hospital admission.
- Treating physician determines the patient is no candidate to receive 2 of the 5 protocol-specified ASM.

5.3. Enrollment/Selection Strategies

5.3.1. Prospective Recruitment

[figure not shown]
The recruitment for this study is based on three steps as shown in Figure 3. The initial prescreening does not imply additional activities to the standard of care and is designed to provide an opportune identification of potential research subjects while they are stable enough to meet the inclusion criteria. The screening period is planned to be short with the application of one additional screening test before enrollment and driven by interaction between the research team and the legally authorized representative (LAR) of the research subject.

By enrollment criteria, the patients from the target population for this study are not able to give consent on their own. Thus, the LAR will be in charge of giving consent on behalf of all the human subjects, including the children. The particularly vulnerable populations of pregnant subjects and prisoners will be excluded from the study. In the particular case of pregnant subjects they will be excluded due to higher risk of study-related pregnancy complications.

Relevant aspects regarding the protection of particularly vulnerable subjects: This research is considered to involve greater than minimal risk but presents the prospect of direct benefit to the individual subjects, thus in the case of children, the consent of one of their parents will be required.

Language recruitment barriers: Informed consent form in Spanish, and Spanish-spoken in-person interview and phone calls by study personnel will be an available alternative for the non-English speaking population that might prefer Spanish to reduce language recruitment barriers.

The recruitment strategy process is described in Figure 3.

5.3.2. Screen Failures

We expect less than 5% of potential subjects will be screen failures because individuals will be screened and enrolled on the same day. That is possible because most of the eligibility criteria will be previously reviewed during the prescreening process. The only screening test is the application of the Barthel Index, which will be done after verbal consent for screening at the time of the in-person interview for the study informed consent. At that time, the screening list will be complete, and the final decision of eligibility for enrollment will be taken before asking for informed consent for the study. Patients deemed ineligible during the interview will not be able to re-screen.

5.4. Strategies for Retention

The primary strategy to prevent dropout during the treatment phase is to keep frequent direct communication with the care team to schedule rs-fMRI #2 as soon as possible by the indicated time frame.

The average SABI patient volume treated last 3 years at the NeuroICU and the PICU at UNC health was 1238 and 109 patients/year respectively (via UNCH operation analyst), for which an adequate volume to cover enrollment is

expected. UNC health has previously enrolled MSABI patients on research and has all the necessary equipment and resources to complete the eligibility evaluations for this study.

5.5. Matching and Stratification

In ICU patients with suppression of consciousness, we will use the routine care EEG to stratify patients into two groups, EEG+ and EEG- during the prescreening. EEG+ will be defined by either electrographic seizure, electroclinical seizure or ictal-interictal continuum as defined by the American clinical Neurophysiology Society's Standardized Critical Care EEG Terminology²⁸, whereas EEG- will be lacking these features. EEG in this protocol does mean continuous video EEG, which is the stand of care for UNCH ICU patients.

To select the patients for screening and enrollment, we will use a quota sampling strategy. Specifically, we will recruit eleven SzNET+ patients consecutively for each EEG+ and EEG- group. Once one of those group's enrollment is complete, we will continue screening only patients from the EEG category that could be enrolled in the incomplete SzNET+ group.

As this is a pilot study, including a wide range of age, the study design does not include matching.

5.6. Randomization and Concealment

This is an open label, nonrandomized study. Not applicable.

5.7. Blinding

The Follow-up EEG will be assessed by an epileptologist blinded to rs-fMRI#2 results. Those results will not be posted in the medical records or commented with personnel outside the clinical rs-fMRI service until the follow up EEG and its comparison results should be collected. This blinding doesn't need to be removed to reassure the patient SOC.

6. Treatment Design: Procedures

Description For this uncontrolled, open-label, interventional trial, the intervention will be assigned to all enrolled patients with SzNET+ by the first rs-fMRI. The intervention and its compliance criteria are defined as receiving treatment for three to ten complete days with at least two of the following ASM regimens, simultaneously:

1. Phenobarbital 20 mg/kg intravenous loading dose
2. Levetiracetam 60mg/kg intravenous loading dose
3. Lacosamide 200 mg intravenous loading dose
4. Valproate 30 mg/kg intravenous loading dose
5. Fosphenyton 20 mg/kg intravenous loading dose

All the maintenance dose regimens will start the next day to loading dose, and dosing will be calculated for weight and age of both medications within the combination group, until the repeat rs-fMRI. As soon as possible, the research team will inform the care team that the patient has been allocated to the intervention branch so they can decide on two ASM regimens from the previous list to start the treatment. On the same day, the research team will confirm by medical charts the two ASM selected and the date and the time of the first loading dose infusions. The intervention phase takes the time between rs-fMRI#1 and follow-up rs-fMRI and EEG. The rs-fMRI#2 must be performed after at least three complete days of treatment and no later than eleven days after the beginning of the intervention phase, but in case of ASM withdrawal, the rs-fMRI#2 must be done no later than 72 hours from the last dose. As outcome measures are based on data collected the day of the second rs-fMRI, after that day, the care team will be free to adjust ASM according to what better fits the patient without compromising the protocol.

The study's main intervention option consists of the Phenobarbital and Levetiracetam regimens. However, the clinical team can select any combination of two or more ASM regimens from the list provided, for clinical reasons. On day two of intervention, the phenobarbital serum level will be measured if it was one of the selected medications, and a new loading dose will be given to aim for a serum level of 40mcg/ml.

Participants with GCS 9 to 12 will not receive phenobarbital as one of the intervention anti-seizure medications (ASM), and the loading dose of one of the two selected ASMs will be omitted. For these participants the study's main intervention option consists of the Levetiracetam and Lacosamide regimens, omitting the Lacosamide loading dose.

Rs-fMRI schedule (Day 0-1 of Enrollment)

- Order Pre-Intervention research-related rs-fMRI#1

Time from enrollment to intervention start (Days 1-6 of Enrollment)

- Scan **should** be performed within 3 days **from enrollment**.
- **To undergo any study indicated rs-fMRI, the participant should not have been diagnosed with vasospasm based on their most recent transcranial Doppler examination, conducted within the last 3 days.**
- The time frame between fMRI scan and intervention start will range from 1 to 6 days.
- Obtain (research driven) fMRI
 - What is rs-fMRI
 - ♦ MRI generates images based on the interaction of the body with potent electromagnetic fields.
 - ♦ Rs-fMRI uses BOLD signal to identify vascular reflexes related to neuronal activation.

- What is the process of transporting the patient to the fMRI?
 - ◆ As SOC at UNC Health, a transport team made of two nurses, one fellow physician and one respiratory therapist gathers with the patients at ICU and checks to have the required equipment for transportation.
 - ◆ The subject is transported by the transport team from the ICU to the MRI Scan within the hospital, located on the first floor or the basement of the same ICU building, according to the MRI scanner availability.
 - ◆ Once the rs-fMRI scanning is acquired the transport team transports the subject back to the ICU.
- How long does the fMRI routinely last?
 - ◆ Around 25 minutes for the scanning
 - ◆ Variable transportation times, from ICU to scanner and from scanner to ICU
- What are the risks associated with the fMRI?
 - ◆ Patients meeting eligibility criteria do not have risk of adverse events related to the electromagnetic fields
 - ◆ Rs-fMRI does not require contrast agents to be administered.
 - ◆ In case of tattoos with suspected high levels of ferromagnetic compounds cold compresses can be applied to prevent heating.
 - ◆ Transportation through the hospital to perform the MRI scan can be associated with mechanical risks and support devices malfunction. Trained personnel is in charge of the process, which is supervised by a physician.

○ SzNET Stratification of rs-fMRI

- SzNET (-): with EEG (+) or EEG (-).
 - ◆ N=32
 - ◆ No protocol Intervention-driven, combined ASM is administered.
 - ◆ They will not receive the second fMRI.
 - ◆ They will only be followed at the 3 months post discharge visit if they are scheduled to one of the NSICU Post-Discharge clinics.
 - ◆ MRI scan transportation related AE Review.
- SzNET(+): with EEG(+).
 - ◆ N=11
 - ◆ Proceed with combined ASM Intervention.
 - ◆ Intervention **must** start within 1 to 6 days after enrollment.
 - ◆ AE Review.
- SzNET(+):with EEG(-)
 - ◆ N=11
 - ◆ Proceed with combined ASM Intervention.
 - ◆ Intervention **must** start within 1 to 6 days after enrollment.
 - ◆ AE Review.

○ Study team will inform the family of the rs-fMRI results and upload the official report to EPIC.

Intervention start (Days 1-6 from Enrollment)

- **Clinical Care Team** will choose the intervention regimen.
 - If participant was already on **two** of the protocol-approved ASM, the participant will be required to start the intervention by administering the protocol-driven loading dose infusions outlined for

each of the combined ASMs, or by administering the loading dose for any of the other 5 listed ASM options. A third option in this case is to administer protocol-driven loading dose of one of the current medications and add another of the 5 ASM loading dose and maintenance regimen.

- If participant was already on **one** of the protocol-approved ASM, the participant will be required to start the intervention by administering the protocol-driven loading dose outlined for the ASM that the participant was previously receiving *along with* another protocol-driven ASM loading dose from the ones listed on the protocol.
- If participant **was not receiving any** of the protocol approved ASM, the participant will be administered a loading dose of two of the 5 protocol approved ASM.
- If the clinical care team does not want to use a combination of two of the 5 protocol-approved ASMs, they will not be enrolled into the study.

- **Research Team** will
 - Review adverse events
 - Review participant medical record to confirm which combined ASM was decided by the clinical care team and charge it into EPIC.
 - Document date and time of first intervention-related loading dose infusions.

Maintenance Dose (Up to 3 to 10 Days from loading dose start)

- **Research Team** will charge to EPIC the maintenance doses and verify ASM Administration.
 - The maintenance protocols must be administered for at least 72 hours from the start time of the loading dose infusion.
 - The MD can continue for up to 10 days while the second fMRI is trying to be scheduled and obtained.
 - The ASM can be continued beyond 10 days but would no longer be considered in the protocol-driven intervention phase.
 - The Post-Intervention assessment scans can be obtained, even if the participant remains on ASM beyond the maintenance dose period.
 - **To undergo any study indicated rs-fMRI, the participant should not have been diagnosed with vasospasm based on their most recent transcranial Doppler examination, conducted within the last 3 days.**
 - If one of the combined doses administered is phenobarbital
 - *On Day 2 of the MD:*
 - ♦ Specimen Collection (phenobarbital serum level UNC Hospitals Test ID LAB30) will be ordered by the research team.
 - ♦ The **research team** reconvenes the maintenance dosing with the **medical care team** to aim for a level of 40mcg/ml.
 - Review any AEs associated with ASM
 - Review Dropout data (if applicable)

- **Medical Care Team** will decide if the patient continues with the study's antiseizure medication regimens. In this case, they will continue to provide the medication, and the patient will be responsible for expenses.

Acquisition, storage and preparation: The present study does not employ experimental compounds, all the medications related to the study follow the same standard Storage rules of the medications regularly used at the ICUs of UNCH.

Administration: IV and enteral administration with infusion times and observation according to the internal protocols for each medication at the patient's corresponding ICU.

Rescue Procedures/Medications

- If emergent adjustments to the treatment plan are needed those will be decided by the care team.
- Administration of additional ASM to the study intervention is allowed as determined by the clinical team.

Adherence Monitoring/Evaluations the intervention's ASM timing and dosing will be checked from the medical charts. On day two, the phenobarbital serum level will be measured if it was one of the selected medications, and a new loading dose will be given to aim for a serum level of 40mcg/ml.

Concomitant Therapies There are no prohibited or recommended concomitant therapies. Calcium channel blockers must be used with precaution when administering some of the protocol ASM (see appendix B & E).

Follow-up tests (Days 3-13 from Start of Loading Dose)

- Order Post-Intervention research-related rs-fMRI (#2)
 - Scan must be **performed** after completing a minimum of 72h of intervention ASM protocol (including loading and maintenance doses).
 - Scan must be **completed** within 72hrs of last intervention ASM dose.
 - **To undergo any study indicated rs-fMRI, the participant should not have been diagnosed with vasospasm based on their most recent transcranial Doppler examination, conducted within the last 3 days.**
 - Post scan, the participant can continue on their current ASM regimen or be changed based on routine clinical care decisions.
 - The official results report will be uploaded to EPIC after the post-intervention research-related EEG has been reported.
 - AE Review:
 - Review Dropout data (if applicable)
 - Collect GCS Score
- Obtain Post-Intervention research-related EEG
 - EEG characteristics
 - The EEG is a non-invasive medical test with very low risk of adverse events. Very rare complications could be associated with skin reactions to the conducting material used for the electrodes and malfunction of the device.
 - Bedside monitoring.
 - Minimum 1 hour run.
 - Without Photostimulation.
 - EEG recording must be obtained within 72hrs of last intervention ASM dose.
 - Post the EEG, the participant can continue on their current ASM regimen or be changed based on routine clinical care decisions.
 - EEG will be reviewed by a blinded epileptologist for rs-fMRI (#2) results.
 - For ethical reasons the results will be shared with the care team.

7. Schedule of Activities and Procedures

